4.1.3 Dose Limiting Toxicity Criteria

A DLT is defined as any of the following events that occur within 28 days starting with the first dose on C1D1 and that is considered to be related to IP. Confirmation of DLTs will be made by the Dose Escalation and Safety Committee (DESC). The severity of AEs will be assessed according to NCI-CTCAE, version 5.0.

DLT is defined as follows:

- Non-hematologic AEs that are \geq grade 3.
- Confirmed Hy's law case.
- New onset of grade 4 thrombocytopenia (with minimum of 2 grade worsening from baseline) within 24 hours of dosing.
- Prolonged myelosuppression, defined as ANC $<$ 500/ μ L for more than 28 days off therapy and in the absence of evidence of active leukemia or MDS in the marrow or blood, will be considered a DLT.

The following AEs will not be considered as DLTs:

- Electrolyte abnormalities that are not associated with clinical sequelae or deemed not clinically significant and corrected with appropriate management or supplementation within 72 hours of onset.
- Grade 3 infusion site reaction if successfully managed and resolved within 72 hours.
- Grade 3 febrile neutropenia with or without infection.
- Alopecia, anorexia or fatigue.
- Grade 3 nausea and/or vomiting if not requiring tube feeding or total parenteral nutrition, or diarrhea and/or constipation if not requiring or prolonging hospitalization that can be

managed to grade \leq 2 with standard antiemetic or antidiarrheal medications used at prescribed doses within 7 days of onset.

- Grade 3 liver function test (LFT) elevations that resolve to \leq grade 1 within 7 days; LFT elevations lasting $>$ 7 days that are considered to be clinically significant and at least possibly related to ASP7517 will be considered to be a DLT.
- Immune-related AEs grade 3 that resolve to \leq grade 1 within 7 days.
- Grade 3 or higher hyperuricemia due to tumor lysis that resolves to \leq grade 1 with medical interventions, including hospitalization with intravenous hydration and/or rasburicase.

Dose evaluation and dose escalation stopping rules based on the BOPIN design with target DLT rate of 0.30 and optimal interval of (0.236, 0.359) are as follows:

Action	Number of Subjects Treated at Current Dose Level					
	3	4	5	6	7	8
Escalate dose if number of subjects with DLT \leq	0	0	1	1	1	1
Stay at current dose level if number of subjects with DLT =	1	1	-	2	2	2
De-escalate if number of subjects with DLT =	2	2	2 or 3	3	3 or 4	3 or 4
Stop if number of subjects with DLT \geq	3	3	4	4	5	5

DLT: dose limiting toxicity

Dose escalation within individual subjects will not be allowed.

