4.1.2 Phase 1 Dose Escalation

The dose escalation portion will assess safety and tolerability of ASP7517. In the dose escalation phase, subjects must be managed under hospitalization for at least 7 days during the first cycle of the dose escalation phase. In addition, prior to hospital discharge, the investigator must ensure subject safety by performing medical tests and procedures listed on day 7 of cycle 1 and tests considered clinically necessary in the opinion of the investigator to evaluate the subject's general condition and AE resolution. The subject should also be followed on an outpatient basis on planned visits during cycle 1 and 2 after hospital discharge during the DLT assessment period to closely monitor any AEs. Subjects may be hospitalized days 1 to 7 during cycle 2 based on investigator opinion.

After dosing of ASP7517, subjects must be observed for safety for a minimum of 4 hours. The safety observation will consist of hourly vital signs and AE observations. If new AEs are observed that are \geq grade 3 during this time, subjects should continue to be observed at the investigator's discretion.

In phase 1 (dose escalation), the starting dose level is 1×10^6 cells/dose and the decision to dose escalate to the next dose levels (1×10^7 and 1×10^8 cells/dose) will be made based on the assessment of safety variables, including the occurrence of dose limiting toxicities (DLTs). Dose escalation will be guided according to the Bayesian optimal interval (BOIN) design [Liu et al, 2015] to determine the next dose level based on DLT occurrence. After the planned number of evaluable subjects have completed the DLT observation period for a given dose level, safety for that dose level will be assessed. Each dose level in the dose escalation phase will enroll a minimum of 3 and may enroll a maximum of 8 subjects with up to 4 evaluable subjects for the initial assessment of each dose level. Enrollment within each dose escalation cohort will be staggered such that there will be 28 calendar days between the treatment initiation of the first subject and the second subject, as well as 14 calendar days between the second subject and the third subject at the same dose level for all escalation cohorts. An interval of 28 calendar days will separate initiation of first dose of study

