treatment for the last subject in a dose cohort from the first subject in the subsequent dose cohort. The 28-day separation is equivalent to the 28-DLT evaluation period. If the decision is made to stay at the current dose level, then an additional 3 or 4 evaluable subjects may be enrolled to the current dose level. Three to 18 subjects will be enrolled in the dose escalation phase. A minimum number of 6 subjects and a maximum number of 8 subjects must be enrolled at the dose level used to determine the maximum tolerated dose (MTD) and the recommended phase 2 dose (RP2D).

Safety data and other available clinical data will be reviewed on an ongoing basis to determine if the study will proceed to the next dose level/phase.

Subject Replacement during Dose Escalation:

Subjects may be replaced in the dose escalation cohort if:

- Subject is discovered to have enrolled without fully satisfying eligibility criteria.
- Subject received less than the planned dose in cycle 1 for reasons other than DLT.
- Subject has no DLT and withdraws from the study before the end of the DLT evaluation period.

The decision regarding replacement of individual subjects will be made by the sponsor with discussions with the treating investigator.

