4.1.4 Dose Escalation and Safety Committee

A DESC consisting of sponsor representatives and investigators will convene once a dose level cohort completes the DLT observation period and data are available for review. Refer to [Section 10.4.1 Dose Escalation and Safety Committee] and DESC charter for additional details.

The DESC will also review the aggregate safety data from the phase 1 dose escalation and the phase 2 expansion cohorts.

Study enrollment and study treatment will be temporarily interrupted during dose escalation pending review of the following:

- Any death that is not related to disease progression occurring within 30 days of receiving investigational product.
- Occurrence of two grade \geq 4 DLTs in 2 study subjects.
- Any grade 4 hypersensitivity reaction/anaphylaxis.

Additional information regarding DESC responsibilities, membership requirements and safety review time points are described in [Section 10.4 Dose Escalation and Safety Committee] and further detailed in the DESC Charter.

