9.2.6 DLT Evaluation Analysis Set

The DLT Evaluation Analysis Set (DEAS) is defined as all subjects in SAF by excluding subjects who meet any of the following criteria:

- Subject is discovered to have enrolled without fully satisfying eligibility criteria.
- Subject received less than the planned dose in cycle 1 for reasons other than DLT.
- Subject has no DLT and withdraws from the study before the end of the DLT evaluation period

The DEAS will be used for the analysis of DLT data.

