10.4 STUDY ORGANIZATION

10.4.1 Dose Escalation and Safety Committee

A DESC consisting of sponsor representatives and investigators will convene once a dose level cohort completes the DLT observation period and data are available for review.

Additional details regarding responsibilities, membership requirements and safety review time points are included in the DESC Charter. The DESC will also review the aggregate safety data from the phase 1 dose escalation and the phase 2 expansion cohorts.

While safety data from the DLT observation period in the escalation cohorts are the minimum safety data needed for the DESC meeting, all available safety findings will be considered by the DESC. The DESC will assess whether a longer DLT observation period is warranted, based on emerging data. Additionally, only when determining RP2D, the DESC may choose a more conservative dosing decision than the MTD selected by BOIN design, based on evaluation of the safety data and other available data.

The decision on the dose level for the next cohort will be based on the BOIN design. Also, MTD will be determined by BOIN from at least 6 subjects with the maximum of 8 subjects under the maximum of 2 cohorts. The dose for phase 2 expansion will not be higher than the MTD.

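### The prolonged-myelosuppression DLT takes more than 28 days to meet but must occur within a 28-day window, and neither the protocol nor the SAP says how to count a case still open at the cohort decision

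*Protocol*

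**What the plan says.** Protocol 4.1.3 opens: "A DLT is defined as any of the following events that occur within 28 days starting with the first dose on C1D1". The event must also be related to the product, and the DESC confirms it. One of the four listed events is ANC below 500/µL "for more than 28 days off therapy and in the absence of evidence of active leukemia or MDS in the marrow or blood". The synopsis (1.1) and SAP 5.2.1 repeat both statements.

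Some exclusions in the same section depend on what happens after onset. Gastrointestinal events are exempt if controlled "with standard antiemetic or antidiarrheal medications used at prescribed doses within 7 days of onset", and liver-test and immune-related events have similar 7-day clauses.

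Protocol 4.1.2 sets the stagger: 28 days between the first and second subject, "as well as 14 calendar days between the second subject and the third subject at the same dose level", then 28 days from the last subject's first dose to the next cohort's first dose. It explains: "The 28-day separation is equivalent to the 28-DLT evaluation period". The same section places outpatient visits in both cycles 1 and 2 within the DLT assessment period.

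Under 4.1.4, the DESC "will convene once a dose level cohort completes the DLT observation period and data are available for review". Section 10.4.1 bases the next cohort's dose on BOIN and adds: "The DESC will assess whether a longer DLT observation period is warranted, based on emerging data". The DLT Evaluation Analysis Set (protocol 9.2.6, SAP 4.6) removes ineligible subjects, under-dosed subjects, and this group: "Subject has no DLT and withdraws from the study before the end of the DLT evaluation period".

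**The concern.** An event that must last more than 28 days cannot be completed in a window that is 28 days long and starts with the first dose. Scheduled dosing makes it worse: dose 2 falls on C2D1, so the off-therapy run ends at about day 28.

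If onset is meant, the rule works, but it matures after the window closes, and the 28-day gap before the next cohort was sized to the window alone. The BOIN table has no column for a subject whose status is still open, and the exclusions in 9.2.6 do not cover one. By default such a subject would sit in the denominator without a DLT.

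DLTs are among the primary safety endpoints, and the BOIN count drives ten-fold dose steps in a first-in-human study. A miscount of this kind runs toward escalation. The same definition feeds the phase 2 safety model (protocol 4.1.5) and the China cohort's BOIN rules (SAP 2.2), so on the literal reading this toxicity would enter none of them.

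**Working it through.** **1. The plan's BOIN figures.** The target is 0.30 and the stated interval (0.236, 0.359). The documents do not give the alternative rates, so I assume the usual 0.6 × 0.30 = 0.18 and 1.4 × 0.30 = 0.42.

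- Lower bound: ln(0.82/0.70) / ln[(0.30 × 0.82)/(0.18 × 0.70)] = 0.2365
- Upper bound: ln(0.70/0.58) / ln[(0.42 × 0.70)/(0.30 × 0.58)] = 0.3585

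Both match. With a stop rule of Pr(rate > 0.30) > 0.95 under a uniform prior, every cell of the table for 3 to 8 subjects reproduces.

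**2. When the criterion is first met.** Count C1D1 as study day 1. A run with onset on day s first exceeds 28 days on its 29th consecutive day, which is day s + 28.

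- s = 1: day 29
- s = 28: day 56

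Counting elapsed days instead adds one day (30 and 57). Neither count falls within days 1-28.

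**3. Follow-up at the next cohort's earliest dose.** Take a three-subject cohort at the minimum stagger. First doses are on calendar days 0, 28 and 42, and the next cohort may start on day 42 + 28 = 70. On the onset reading, with dose 2 held:

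| Subject | Days of follow-up | Study day reached | Onsets resolved | Onsets still open |
|---|---|---|---|---|
| 1 | 70 | 71 | days 1-28 | none |
| 2 | 42 | 43 | days 1-15 | days 16-28 |
| 3 | 28 | 29 | day 1 | days 2-28 |

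On the elapsed-day count, the open ranges become days 15-28 and days 1-28. With four subjects, no interval is set between the third and fourth. If they are dosed together, the dates do not change. If the fourth starts 14 days later, follow-up is 84, 56, 42 and 28 days, and the problem moves to subjects 3 and 4.

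**4. Effect on the decision.** From the plan's table, 1/3 and 1/4 are stay while 0/3 and 0/4 are escalate; 2/6 is stay while 1/6 is escalate. One open case that later matures is enough to cross the line.

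**5. How often.** The documents give no frequency. Let q be the event rate and p the rate of any other DLT, with subjects independent, dose 2 held and onset spread evenly over 28 days. A false 0/3 (none observed, at least one true) has probability

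(1 − p)³ × [(1 − q)(1 − 15q/28)(1 − q/28) − (1 − q)³]

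- p = 0.20, q = 0.01: 0.0072
- p = 0.10, q = 0.05: 0.0478

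If onset is always by day 15, the bracket becomes (1 − q)²(1 − q/15) − (1 − q)³, and the results are 0.0047 and 0.0307.

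**6. How many subjects are exposed at the higher dose.** The 28-day gap between first and second subjects applies at every dose level. If the last subject of a cohort is dosed on day L, the latest open case resolves on day L + 55. The second higher-dose subject cannot start before L + 28 + 28 = L + 56. Here L = 42, so resolution falls on day 97 against day 98 (day 98 on the elapsed-day count). At most one subject is treated at the higher dose first.

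**The case against.** The strongest reply is that the text already leans toward onset. The 7-day clauses and the placing of cycle 2 visits in the DLT assessment period both point that way. The DESC confirms DLTs, waits for data, considers all available safety findings and must assess whether a longer observation period is needed; an open severe neutropenia is an obvious case for it. Table 1 schedules a predose C2D1 marrow, which would settle many cases at about day 29 by showing active disease. Section 6.6 withholds the next dose after a related grade 3 event. The event also needs relatedness and no active disease, which should be uncommon in a relapsed or refractory population.

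Most of this stands, and it is why the expected impact is low. It does not repair the definition. The onset reading has to be inferred. The DESC's power to lengthen observation is discretionary and not tied to this criterion, while 10.4.1 bases the next cohort's dose on BOIN and allows a more conservative choice only at RP2D selection. Section 6.6 names only grade 3 events. The C2D1 marrow can close a case by showing disease, but it cannot confirm one.

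A reader might infer that a whole cohort could be treated at too high a dose, or that nothing anywhere deals with an open case. The documents do not support either. The next cohort's own stagger limits the exposure (step 6). The absence of a pending rule is established only for the protocol and SAP; the DESC Charter, which holds further detail on safety reviews, was not available. Nor does any text say that an open case is counted as DLT-free. That follows from the lack of any other category.

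**Conclusion.** Wrong as written, with low expected impact. Read literally, a listed DLT can never count. On the likelier onset reading, cases in the second and third subjects can be open at the earliest next-cohort dose, and in the third subject this applies to nearly every onset, not only late ones.

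With assumed event rates of 1% to 5% and other-DLT rates of 10% to 20%, a false 0/3 has a chance of 0.7% to 4.8%, or 0.5% to 3.1% if onset is by day 15. All of these rates and both onset patterns are assumptions. The starting dose is expected to have minimal activity (4.1.6), so the lower part of the range is more plausible there. Day 70 is the earliest date; waiting for data would shorten or close the gap.

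The exposure is confined to the cohort decision and, at the minimum stagger, to at most one subject at the higher dose. On the onset reading, a case confirmed later can still enter the MTD estimate and the phase 2 safety model.

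**What to change.** Amend protocol 1.1, 4.1.3 and 9.2.6, and SAP 4.6 and 5.2.1.

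Definition:

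> ANC below 500/µL with onset within 28 days of C1D1, lasting more than 28 days from onset, off therapy, with neither marrow nor blood showing active leukemia or MDS, is a DLT.

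Pending rule:

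> A subject with ANC below 500/µL at day 28, with onset in the window and no active disease on the scheduled predose C2D1 marrow and blood, is pending. Dose 2 is held. The subject is not counted as DLT-free in the BOIN count until ANC recovers, active disease is shown, or the run exceeds 28 days (about day 56 at the latest).

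If the Charter already has such a rule, the protocol and SAP should state it too, because the definition sits there.

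The cost is wording plus, only when such a subject occurs, a wait of up to about 4 weeks before the cohort decision (study day 29 to day 56 in the last subject). That subject may also lose dose 2, because a delay of more than 2 weeks for related toxicity ends treatment (8.1.1). Follow-up continues after discontinuation (8.2), so the event can still be confirmed.

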Dose escalation will be guided according to the Bayesian optimal interval (BOIN) design [Liu et al, 2015] to determine the next dose level based on DLT occurrence. After the planned number of evaluable subjects have completed the DLT observation period for a given dose level, safety for that dose level will be assessed. Each dose level in the dose escalation will enroll a minimum of 3 and may enroll a maximum of 8 subjects with up to 4 evaluable subjects for the initial assessment of each dose level. Refer to [Section 9.2.6 DLT Evaluation Analysis Set] for definition of evaluable subjects. Enrollment within each dose escalation cohort will be staggered such that there will be 28 calendar days between the treatment initiation of the first subject and the second subject, as well as 14 calendar days between the second subject and the third subject at the same dose level for all escalation cohorts. An interval of 28 calendar days will separate initiation of first dose of study treatment for the last subject in a dose cohort from the first dose of the first subject in the subsequent dose cohort. The 28-day separation is equivalent to the 28-DLT evaluation period. If the decision is made to stay at the current dose level, then an additional 3 or 4 evaluable subjects may be enrolled to the current dose level. Three to 18 subjects will be enrolled in the dose escalation phase. A minimum number of 6 and a maximum number of 8 subjects must be enrolled at the dose level used to determine the maximum tolerated dose (MTD) and the recommended phase 2 dose (RP2D).

Study enrollment and study treatment will be temporarily interrupted during dose escalation pending review of the following:

- Any death that is not related to disease progression occurring within 30 days of receiving investigational product.
- Occurrence of two grade \geq 4 DLTs in 2 study subjects.
- Any grade 4 hypersensitivity reaction/anaphylaxis.

Dose Escalation and Safety Committee:

A Dose Escalation and Safety Committee (DESC) consisting of sponsor representatives and investigators will convene once a dose level cohort completes the DLT observation period and data are available for review. Additional details regarding responsibilities, membership requirements and safety review time points are included in the DESC Charter. The DESC will also review the aggregate safety data from the phase 1 dose escalation and the phase 2 expansion cohorts.

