9.5.7 Dose Limiting Toxicities

A DLT event, as defined in [Section 4.1.3 Dose Limiting Toxicity Criteria], will be summarized by dose level using DEAS. Details of DLTs will be presented in listings and subject narratives.

DLT review for dose escalation decisions and declaration of DLT and MTD will be performed for each dose level throughout the trial. Dose escalation decisions will be guided by BOPIN as described in [Section 4.1.3 Dose Limiting Toxicity Criteria].

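### The BOIN decision table is indexed by subjects treated, while the rules that feed it count DLT-evaluable subjects; at 1 DLT in 4 evaluable of 5 treated, the header turns stay into escalate

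*Protocol*

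**What the plan says.** The decision table appears three times (Protocol 1.1, Protocol 4.1.3, SAP 5.2.1), each time with columns 3 to 8 under the header "Number of Subjects Treated at Current Dose Level". No sentence says that treated means DLT-evaluable there.

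The table carries weight. Protocol 9.5.7 states: "Dose escalation decisions will be guided by BOPIN as described in [Section 4.1.3 Dose Limiting Toxicity Criteria" (BOPIN and BOIN are used for the same design). Protocol 10.4.1 adds: "The decision on the dose level for the next cohort will be based on the BOIN design".

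The rules that bring a dose level to the table count evaluable subjects:

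- Timing of review (Protocol 4.1.2): "After the planned number of evaluable subjects have completed the DLT observation period for a given dose level". The same section allows up to 4 evaluable subjects at the first look.
- Definition (Protocol 1.1): "Refer to [Section 9.2.6 DLT Evaluation Analysis Set] for definition of evaluable subjects".
- After a stay decision (Protocol 4.1.2): "then an additional 3 or 4 evaluable subjects may be enrolled to the current dose level".
- MTD (Protocol 1.1 and SAP 5.2.2): at least 6 evaluable subjects.
- DLT analysis (Protocol 9.2.6): "The DEAS will be used for the analysis of DLT data".

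Some counts are not in evaluable subjects. The cap of 8 per dose level and the range of 6 to 8 at the MTD/RP2D dose (Protocol 4.1.2) refer to enrolled subjects, and Protocol 10.4.1 bases the MTD on at least 6 plain subjects.

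**The concern.** Treated and evaluable counts can differ by design. One of the three reasons for replacement in Protocol 4.1.2 is "Subject has no DLT and withdraws from the study before the end of the DLT evaluation period". The same three reasons exclude a subject from the DEAS in Protocol 9.2.6. Such a subject has been treated, so a literal reader moves one column to the right and divides the same number of DLTs by a larger number.

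The rule governs a first-in-human product. The dose steps are ten-fold (Protocol 4.1.2) and no NOAEL was determined (Protocol 2.1.1.3). An index that can turn stay into escalate should not depend on inference.

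**Working it through.** **Inputs.** Target DLT rate 0.30, interval (0.236, 0.359) and the printed cells (Protocol 4.1.3); cohort sizes (Protocol 4.1.2). Two assumptions are not stated in the documents: the usual BOIN spacing of 0.6 and 1.4 times the target, and a stop rule of P(rate > 0.30 | data) > 0.95 under a uniform prior.

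**Step 1: reproduce the plan's figures.** With φ = 0.30, φ1 = 0.18 and φ2 = 0.42:

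- Escalation limit = ln[(1−φ1)/(1−φ)] / ln[φ(1−φ1)/(φ1(1−φ))] = ln(0.82/0.70) / ln(0.246/0.126) = 0.2365.
- De-escalation limit = ln[(1−φ)/(1−φ2)] / ln[φ2(1−φ)/(φ(1−φ2))] = ln(0.70/0.58) / ln(0.294/0.174) = 0.3585.

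Both match the stated interval. With the assumed stop rule, every printed cell for n = 3 to 8 is reproduced, so the thresholds are correct.

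**Step 2: list the planned looks.** A first cohort of 3 or 4, extended by 3 or 4, gives 3, 4, 6, 7 or 8 evaluable subjects. Five is not a planned count; column 5 comes into use mainly when treated and evaluable counts differ.

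**Step 3: compare columns when one treated subject without a DLT is non-evaluable.**

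| Evaluable of treated | DLTs where the action changes | By evaluable count | By header |
|---|---|---|---|
| 3 of 4 | none | – | – |
| 4 of 5 | 1 | stay | escalate |
| 4 of 5 | 3 | stop | de-escalate |
| 6 of 7 | 4 | stop | de-escalate |
| 7 of 8 | none | – | – |

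The reasons are numerical. 1/4 = 0.25 lies inside the interval and 1/5 = 0.20 lies below it. P(rate > 0.30) is 0.969 for 3/4 and 0.930 for 3/5; it is 0.971 for 4/6 and 0.942 for 4/7.

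**Step 4: size, given 4 evaluable of 5 treated and no DLT in the non-evaluable subject.** Let p be the true DLT rate, independent across the 4 evaluable subjects. Column 4 escalates at 0 DLTs, with probability (1−p)^4. Column 5 escalates at 0 or 1, with probability (1−p)^4 + 4p(1−p)^3.

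| p | Column 4 | Column 5 | Difference, 4p(1−p)^3 |
|---|---|---|---|
| 0.10 | 0.656 | 0.948 | 0.292 |
| 0.20 | 0.410 | 0.819 | 0.410 |
| 0.30 | 0.240 | 0.652 | 0.412 |
| 0.40 | 0.130 | 0.475 | 0.346 |

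At 0.10 and 0.20 the true rate is below the escalation limit, so escalating is what the design intends. The rows that bear on safety are 0.30 and 0.40.

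**Step 5: the smaller changes.** Three DLTs in 4 has probability 4p³(1−p) = 0.076 at p = 0.30 and 0.154 at 0.40. Four DLTs in 6, after a stay at 1 in 3, needs 3 in the next 3: p³ = 0.027 and 0.064. Under either reading, stop or de-escalate, the next cohort does not receive that dose.

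**Step 6: direction.** If the excluded subject was ineligible and had a DLT, the effect can reverse. With no DLT in 3 evaluable subjects, column 3 says escalate; with 1 DLT in 4 treated, column 4 says stay.

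**The case against.** The strongest reply is that the documents already supply the denominator. The synopsis paragraph that introduces BOIN refers to the DEAS definition, Protocol 9.2.6 assigns DLT data to the DEAS, and Protocol 9.5.7 names the DEAS in the same section that sends escalation decisions to the table. This stands as to intent: column 4 is the intended reading. It does not repair the header, which is the only text that says what the columns count.

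A second reply is that the main case is narrow. It needs a planned cohort of 4 and a replacement; without replacement, or with a planned cohort of 3 and one replacement, the count is 3 of 4 and nothing changes. Someone replaced in the cohort might also naturally drop out of its count. The narrowness stands. The last step is again an inference, because a replaced subject has still been treated.

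A third reply is that the Dose Escalation and Safety Committee (DESC) considers all available safety findings and has a charter. The charter is not among the documents and may settle the count. Protocol 10.4.1, however, lets the committee be more conservative than the BOIN-selected MTD only when it determines the RP2D.

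A reader might infer more than the documents support: that the whole plan except this table counts evaluable subjects, that the thresholds are wrong, or that the header always gives the less cautious action. Enrolment limits and some minimums count other things, the cells reproduce, and Step 6 shows a reversal.

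**Conclusion.** The point holds as a labelling error of minor severity in a rule that drives dose decisions. The wording mismatch is certain. A wrong dose decision is only possible, and it requires three things together: a first cohort planned at 4, one non-evaluable subject without a DLT who is replaced, and a committee that reads the header literally against the DEAS wording. Given all three, the chance of escalating rises from 0.24 to 0.65 at a true DLT rate of 0.30 and from 0.13 to 0.48 at 0.40.

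These are conditional figures. The documents give no rate of non-evaluable subjects, so they cannot be read as the chance that the trial escalates wrongly. SAP 2.2 sends the China cohort to the same rules, but the China-specific amendment is not available and no separate claim is made for that cohort.

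**What to change.** Change the column header to *Number of DLT-evaluable subjects (DEAS) at current dose level* in Protocol 1.1, Protocol 4.1.3 and SAP 5.2.1. Leave every cell as printed. The cost is one header in three places, with no effect on design, sample size or analysis. If the DESC charter reproduces the table, its header should match.
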